[REDACTED]

Sponsor's Medical Monitor
[REDACTED]
[REDACTED]
[REDACTED]
[REDACTED]

STUDY SYNOPSIS

Study ID:	ADVM-043-03
Study Title:	Post-treatment long-term follow-up study of ADVM-043 gene therapy in alpha-1 antitrypsin deficiency
Sponsor:	Adverum Biotechnologies, Inc.
Indication:	Alpha-1 Antitrypsin (A1AT) Deficiency
Phase of Development:	2
Objectives:	
Primary objective
 
Assessment of the long-term safety of ADVM-043
Endpoints:	
Primary endpoint
 
Type, frequency, severity, duration, and relationship to ADVM-043 of adverse events of interest and serious adverse events related to ADVM-043
Study Design:	
This is a long-term follow-up study in subjects with A1AT deficiency who have previously received ADVM-043 gene therapy in a clinical study.
 
Subjects will be followed for up to 3 years post-treatment with ADVM-043.

Study Duration:	Subjects will be assessed for up to 3 years post-treatment with ADVM-043. The duration of this long-term follow-up period is 2 years.
Entry Criteria:	
Inclusion Criteria
 
The subject has A1AT deficiency and has previously received ADVM-043 gene therapy 
Exclusion Criteria
 
The subject is unwilling or unable to participate in all required study evaluationsThe subject is participating in another investigational treatment protocolThe subject is unable to understand the purpose and risks of the study or cannot provide a signed and dated informed consent form (ICF)

Study Population:	Subjects with A1AT deficiency who were previously treated with ADVM-043 in any clinical study
Safety Evaluation:	Evaluations will include assessment of adverse events

TABLE OF CONTENTS

CLINICAL STUDY PROTOCOL	1
1.0 BACKGROUND	10
1.1 Study Population.....	11
2.0 OBJECTIVES AND ENDPOINTS	11
2.1 Objectives	11
2.1.1 Primary Objective:	11
2.2 Endpoints	11
2.2.1 Primary Endpoint	11
3.0 INVESTIGATIONAL PLAN.....	11
3.1 Study Design.....	11
3.2 Study Duration.....	11
3.3 Study Termination	11
3.4 Concomitant Medications	11
4.0 SUBJECT SELECTION AND WITHDRAWAL	12
4.1 Inclusion Criteria	12
4.2 Exclusion Criteria	12
4.3 Subject Withdrawal.....	12
5.0 STUDY ASSESSMENTS	13
5.1 Screening Assessment.....	13
5.2 Year 1 Assessment through Year 2 Assessment.....	13
6.0 ASSESSMENT OF SAFETY	13
6.1 Safety Parameters.....	13
6.2 Definition of an Adverse Event	13

1.0 BACKGROUND

A clinical research subject who has been exposed to an investigational gene therapy may be at risk for delayed adverse events because of the vector that delivers the transgene or because of persistent biological activity of the investigational medicinal product. Some adverse events could be delayed by months or years. Therefore, to mitigate those risks, and per the United States Food and Drug Administration recommendations for the long-term follow-up observation of subjects who received gene therapy products, Study ADVM-043-03 is to be conducted in subjects previously treated with ADVM-043 and will follow them for a total of 3 years post treatment.

The advantage of adeno-associated viral (AAV) vectors in gene therapy is the low propensity of vector genome integration in the host DNA. However, recently there has been attention to potential AAV-induced genotoxicity from systemic or liver-directed gene therapy. To date, mouse studies have varied in their findings in neonatal, juvenile, and adult animals.

AAV genome integration has been observed in neonatal mice that demonstrated a higher risk of developing hepatocellular carcinoma after AAV administration (Bell 2005; Chandler 2015). This insertional mutagenesis to an oncogenic locus (Rian) reported after neonatal gene delivery is thought to be influenced by higher transcriptional activity of that locus during the neonatal period of development, as juvenile and adult rodents have not demonstrated similar findings. Furthermore, the site of AAV integration in mice has no analogue in humans (Bell 2005; Chandler 2015). Long-term larger animal studies in dogs (through 8 years) and nonhuman primates (through 5 years) have not shown such genotoxicity (Niemeyer 2009; Nathwani 2011).

To date, there has been no evidence of tumor formation or long-term hepatotoxicity in a hemophilia B gene therapy trial where 10 subjects were treated with systemic AAV. The study demonstrated durable and stable expression of transgenic factor IX at therapeutic levels for at least 4 years after vector delivery (Nathwani 2014).

In alpha-1 antitrypsin (A1AT) deficiency, intramuscular delivery of an AAV1 vector containing a functional A1AT transgene was administered to 18 human subjects (Gruntman 2015). One of the subjects in the highest dose group followed for at least 5 years post-treatment for safety and protein expression still demonstrated measurable A1AT levels without any negative sequelae (Mueller 2017). This suggests gene therapy has the potential for long-term protein expression and consequent disease impact.

Study ADVM-043-03 is a post-treatment long-term follow-up study intended to collect safety data in subjects with A1AT deficiency who received ADVM-043 in a prior treatment study.

No investigational agent will be administered in Study ADVM-043-03.

1.1 Study Population

The study population will comprise of subjects with A1AT deficiency who were previously treated with ADVM-043 in any clinical study.

2.0 OBJECTIVES AND ENDPOINTS

2.1 Objectives

2.1.1 Primary Objective:

- Assessment of the long-term safety of ADVM-043

2.2 Endpoints

2.2.1 Primary Endpoint

- Type, frequency, severity, duration, and relationship to ADVM-043 of adverse events (AEs) of interest and serious adverse events (SAEs) related to ADVM-043

3.0 INVESTIGATIONAL PLAN

3.1 Study Design

This is a long-term follow-up study in subjects with A1AT deficiency who have previously received ADVM-043 gene therapy in a clinical study. Subjects will be followed for up to 3 years post-treatment with ADVM-043.

3.2 Study Duration

Subjects will be assessed for up to 3 years post-treatment with ADVM-043. The duration of this long-term follow-up period is 2 years.

3.3 Study Termination

The Sponsor reserves the right to terminate the study, or any part of the study, at its discretion for any reason. Should this be necessary, both the Sponsor and the Investigator will arrange the discontinuation procedures. If this study is terminated, the Sponsor and the Investigator will ensure that adequate consideration is given to the protection of the subject's interests.

3.4 Concomitant Medications

There are no prohibited medications.

Any use of protein augmentation therapy for the treatment of A1AT deficiency should be recorded in the case report form (CRF), including any change in its use, such as initiation, discontinuation, holding the dose or change in dosage.

Exposure to known mutagenic medications or agents (Appendix 2) should be recorded in the CRF.

Concomitant medications used to treat AEs of interest and SAEs related to ADVM-043 are to be recorded in the CRF. Other concomitant medications do not need to be recorded.

4.0 SUBJECT SELECTION AND WITHDRAWAL

4.1 Inclusion Criteria

- 1) The subject has A1AT deficiency and has previously received ADVM-043 gene therapy.

4.2 Exclusion Criteria

- 1) The subject is unwilling or unable to participate in all required study evaluations.
- 2) The subject is participating in another investigational treatment protocol.
- 3) The subject is unable to understand the purpose and risks of the study or cannot provide a signed and dated informed consent form (ICF).

4.3 Subject Withdrawal

A subject may withdraw from the study at any time and for any reason without prejudice to their future medical care by the Investigator or at the clinical study site.

Withdrawal from the study will occur under the following circumstances:

- Death
- Withdrawal of consent
- Lost to follow-up
- Study termination by Sponsor

If a subject is lost to follow-up, a minimum of two attempts should be made by the study site personnel to contact the subject. Appropriate contact includes 2 documented phone calls followed by a registered letter before a subject may be listed as lost to follow-up. The measures taken for follow-up and reason for premature study discontinuation should be documented in source documents and CRF.

When a subject withdraws from the study, the reason(s) for withdrawal are to be recorded on the CRF. Whenever possible, all subjects who withdraw from the study are to be encouraged to undergo the End-of-Study assessments at the time of withdrawal.

Sites should obtain follow-up data on any subject who withdraws from the study and has ongoing AEs of interest or SAEs related to ADVM-043. In every case, efforts must be made to undertake protocol-specified safety follow-up procedures.

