5.0 STUDY ASSESSMENTS

Assessments may be conducted in the clinic or remotely via telephone call by site personnel. A subject is required to sign an IRB/IEC approved ICF before any study assessments are performed. Refer to the Schedule of Assessments in Appendix 1.

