15.0 APPENDICES

15.1 Appendix 1 Schedule of Assessments

Assessment ^a	Post-Treatment Assessment Timepoints			
	Screening ^b	Year 1 ^b [REDACTED]	Year 2 [REDACTED]	Year 3 (EOS) ^c [REDACTED]
ICF	X			
Inclusion/ Exclusion Criteria	X			
Review and record exposure to other investigational therapies	X	X	X	X
Record AEs of interest/related SAEs	X	X	X	X
Record conmeds ^d	X	X	X	X

Abbreviations: AE=adverse event; conmed=Concomitant medication; EOS=End-of-Study visit; ICF=Informed Consent Form; SAE=serious adverse event; [X]=optional.

- a Assessments may be conducted in the clinic or with a phone call by site personnel.
- b The Screening Assessment should be completed on the same day as the End-of-Study Visit in the prior ADVM-043 treatment study.
- c End-of-Study (EOS) Assessment is scheduled at 3 years post-treatment [REDACTED], or within [REDACTED] after subject withdrawal.
- d Only concomitant medications for A1AT deficiency (i.e., augmentation therapy), known mutagenic medications / agents, and medications to treat AEs of interest and SAEs related to ADVM-043 should be recorded.

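### Protocol 4.3 lets a missed yearly assessment, two failed calls and a letter lead to withdrawal, with no stated retry, vital-status check or re-entry, while the subject still counts as event-free

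*Protocol*

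**What the plan says.** Protocol 4.3 opens its list with "Withdrawal from the study will occur under the following circumstances" and names loss to follow-up beside death, withdrawal of consent and termination by the sponsor. It first requires that "a minimum of two attempts should be made by the study site personnel to contact the subject", and then specifies: "Appropriate contact includes 2 documented phone calls followed by a registered letter before a subject may be listed as lost to follow-up".

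Two sentences in the same section deal with subjects who have left. One is specific: "Sites should obtain follow-up data on any subject who withdraws from the study and has ongoing AEs of interest or SAEs related to ADVM-043". The other is general: "In every case, efforts must be made to undertake protocol-specified safety follow-up procedures".

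Protocol 3.2 sets follow-up at up to 3 years after treatment and adds: "The duration of this long-term follow-up period is 2 years". Appendix 1 schedules Screening, Year 1, Year 2 and Year 3, with AEs of interest and related serious AEs (SAEs) recorded at each. Its footnote c places the End-of-Study assessment either at 3 years or within a set time after withdrawal. Protocol 5.0 allows telephone contact: "Assessments may be conducted in the clinic or remotely via telephone call by site personnel".

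In the SAP, section 8.1 rules out imputation. Section 9 defines the FAS by prior treatment and eligibility, not by completed follow-up. Section 11.7 bases the safety summaries on the FAS.

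**The concern.** The study exists because harm from gene therapy may appear months or years later. Its AEs of interest include neurologic disorder and unexpected hospitalisation. These, and death, are plausible reasons why a subject does not answer a call or a letter, so loss may be related to the outcome being measured.

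A site that meets the stated minimum at Year 2 has complied with the protocol and may withdraw the subject. Nothing visible then tells it to try again at Year 3, to ask a relative or the treating physician, or to find out whether the subject is alive. Protocol 6.10 asks for an autopsy after a death, but no stated step would bring the death of an unreachable subject to the site's notice.

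In the tables, that subject remains in the denominator and adds nothing to the numerator. The reported AE frequency can then be too low, and the tables would not show by how much.

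**Working it through.** The plan gives no sample size, dropout rate or event rate (SAP 4.2 is marked not applicable), so there is no figure of its own to reproduce. The check is follow-up arithmetic plus labelled illustrations.

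**1. Entry time.** Total follow-up is 3 years after treatment and this study covers 2 (Protocol 3.2). Entry is therefore at about 3 − 2 = 1 year. A subject who left the treatment study early may enter sooner, because Protocol 5.1 ties Screening to that study's last visit whether or not it was completed.

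**2. Follow-up left unobserved if contact is not resumed.** Yearly spacing is assumed, because the visit windows are redacted. Unobserved share = (3 − year of last contact) / 2.

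- Lost at Year 2, last contact at Year 1: (3 − 1)/2 = 2 of 2 years, 100%.
- Lost at Year 3, last contact at Year 2: (3 − 2)/2 = 1 of 2 years, 50%.

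The Screening and Year 1 records remain in both cases.

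**3. Effect on a reported percentage.** The denominator is the whole FAS, N. If a share L of the FAS is lost and a proportion p of those lost have an unseen event (in subjects with no event already recorded), the reported percentage of subjects falls short by L × p. With one subject lost, L = 1/N, so the shortfall is at most 1/N.

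**4. Illustration with assumed N, one subject lost at Year 2.** The share of person-years lost is 2/(2N) = 1/N. The last two columns are the exact one-sided 95% upper bound on the event proportion when no events are seen, 1 − 0.05^(1/m), first with m = N and then with m = N − 1. The SAP plans no such bound; it is used here only to show how much information goes.

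| Assumed N | Person-years lost | Bound, all followed | Bound, one lost |
|---|---|---|---|
| 3 | 33% | 63% | 78% |
| 6 | 17% | 39% | 45% |
| 10 | 10% | 26% | 28% |
| 20 | 5% | 14% | 15% |

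**5. What a retry could recover.** Assume 10% to 30% of subjects are listed as lost at Year 2, and half of them can be reached at Year 3 and asked about the whole gap. Recovery is then 0.10 × 0.5 = 5% to 0.30 × 0.5 = 15% of planned person-time. Both rates are assumptions.

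**6. A knock-on gap in SAP 10.6.** Study periods are bounded by actual visit dates. If Year 2 is missed and an event from that interval is learned of at Year 3, there is no Year 2 date to test it against. Neither the Year 1 to Year 2 period nor the Year 2 to Year 3 period can be assigned.

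**The case against.** A reader might infer that two unanswered calls end follow-up for good and erase the subject's long-term data. The documents do not support that.

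- **Permanence is inferred.** The attempts are a minimum, and listing a subject as lost is permitted, not required. No passage bars later contact.
- **The trigger is more than one missed call.** It takes a missed assessment, two failed documented calls and a failed registered letter.
- **Nothing collected is erased.** Earlier records stay in the analysis and the subject stays in the FAS. What is lost is later person-time, not a member of the cohort.
- **Other safeguards may exist out of sight.** Protocol 6.6 defers a plan of scheduled visits with a health care professional to a study manual that is not among the documents. Consent pages were removed before review. It can be said only that no other route is stated.
- **Recovery by a late call is not assured.** Protocol 5.2 states a look-back to the previous assessment only for investigational therapies, not for AEs, and a call to the subject cannot by itself reveal that subject's death.
- **Some reporting already exists.** SAP 11.2 tabulates attendance by visit, and SAP 11.1 tabulates loss to follow-up and study duration.

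All of this stands, and it narrows the point. It does not close the gap. The general duty, "In every case, efforts must be made to undertake protocol-specified safety follow-up procedures", refers to specified procedures, and none is specified for a subject who cannot be reached. The specific duty covers only events already ongoing, so it would not find a new malignancy or a death. Footnote c of Appendix 1 lets withdrawal set the timing of the End-of-Study assessment, which gives a site little reason to call again at Year 3. The pair of sentences on attempts is a minor matter: the second reads naturally as spelling out the first.

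**Conclusion.** The concern holds as a gap in the stated procedure. A site following the visible text can stop observing a subject after Year 1, and the SAP will count that subject as event-free for the rest of the study. Per subject, the loss is 2 of the 2 years after Year 1 if it occurs at Year 2, and 1 of 2 if it occurs at Year 3. This assumes entry at about one year, yearly spacing and no resumed contact.

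The direction of bias in AE frequency is downward whenever an event is missed, and more so if the event is the reason for the silence. The overall size cannot be derived, because enrolment, dropout and later reachability are not in the documents; the percentages for assumed N and the 5% to 15% recovery are illustrations only. The change is worth making because the stated rule is weak for a study of delayed events and a better one costs little.

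**What to change.** **Protocol 4.3.** Treat a missed yearly contact as a missed visit. Require the site to try again at every remaining timepoint. Assign final loss to follow-up only after the Year 3 attempts, two calls plus a registered letter, have failed.

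**Screening and consent.** Record alternate contacts and the treating physician, with the subject's consent to ask them and to check vital status by Year 3. If the study manual or consent form already provides for this, refer to it in 4.3.

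**Protocol 5.2.** State that a late contact collects AEs of interest and related SAEs since the last successful contact.

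**SAP 10.6.** Add a rule that assigns a study period to an event whose closing visit was missed, for example by the scheduled visit date.

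**SAP 11.1.** Add the date of last known status. The existing attendance and discontinuation tables otherwise suffice.

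The cost is protocol, consent and SAP wording, a vital-status check, and a few extra calls per missing subject. No new visits or procedures are needed.

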5.0 STUDY ASSESSMENTS

Assessments may be conducted in the clinic or remotely via telephone call by site personnel. A subject is required to sign an IRB/IEC approved ICF before any study assessments are performed. Refer to the Schedule of Assessments in Appendix 1.

5.1 Screening Assessment

The Screening Assessment should be completed on the same day as the End-of-Study Visit in the prior ADVM-043 treatment study, irrespective of whether the subject completes the prior treatment study.

The following evaluations are to be conducted at the Screening Assessment:

- Informed consent
- Review of inclusion/exclusion criteria (re-confirm prior to enrollment at the Year 1 assessment)

5.2 Year 1 Assessment through Year 2 Assessment

At each assessment, the following evaluations will be conducted:

- Review and record AEs of interest (Section 6.2), including type, frequency, severity, and relationship to ADVM-043
- Review SAEs related to ADVM-043 including type, frequency, severity
- Review and record any use of augmentation therapy, including any change in its use, such as initiation, discontinuation, holding dose, or change in dosage
- Review and record any exposure to known mutagenic medications or agents (Please refer Appendix 2 Mutagenic Medications / Agents)
- Review and record if the subject has been exposed to any new investigational therapies since the last assessment

6.0 ASSESSMENT OF SAFETY

6.1 Safety Parameters

- Adverse events

6.2 Definition of an Adverse Event

An AE is any untoward medical occurrence in an enrolled subject, regardless of its causal relationship to the investigational medicinal product. Only AEs of interest should be collected and reported.

AEs of interest include the following:

- new malignancy
- new incidence or exacerbation of a pre-existing neurologic disorder
- new incidence or exacerbation of a prior rheumatologic or other autoimmune disorder
- unexpected hospitalization

6.3 Definition of a Serious Adverse Event

An SAE is any untoward medical occurrence in an enrolled subject that results in death; is immediately life-threatening; requires inpatient hospitalization or prolongation of existing hospitalization; results in persistent or significant disability or incapacity; or is a congenital anomaly or birth defect. Only SAEs related to ADVM-043 should be collected and reported.

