6.5 Assessment of Causality

The Investigator's assessment of relationship of an AE to ADVM-043 is part of the documentation process, but it is not a factor in determining what is or is not reported. If there is any doubt as to whether a clinical observation is an AE, the event is to be reported.

Investigator should assess potential causes of each AE and events should be considered related if there is “a reasonable possibility of a causal relationship” rather than if “a causal relationship cannot be ruled out.” When assessing causality, Investigators should assess biological balancing — the probability that the suspect drug caused the AE must be weighed against the probability that an alternative candidate caused it.

Causality of AEs should be assessed in relation to ADVM-043, and not prior concomitant medications or study procedures in the previous treatment study. The relationship or association of ADVM-043 in causing or contributing to the AE is to be characterized using the following criteria:

- Definitely Related: A definite causal relationship exists between study drug administration and the AE; including a plausible time relationship to study drug administration, and it cannot be explained by underlying or concurrent disease or other drugs/exposures.
- Likely Related: There is a reasonable possibility that the study drug caused the AE; the event is unlikely attributed to underlying or concurrent disease or other drugs/exposures (i.e., alternative explanation). There is a reasonable time sequence to administration of the study drug.
- Unlikely Related: Underlying or concurrent disease or other drugs/exposures provide plausible alternative explanations. Temporal relationship to study drug administration makes a causal relationship improbable.
- Not Related: There is no association between the study drug and the reported event; there is a clear alternative explanation; a causal relationship is non-plausible.

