6.8 Serious Adverse Event Reporting

SAEs related to ADVM-043 should be recorded on the CRF by the Investigator or designee (Section 6.3). The Investigator must report a related SAE to the Sponsor within 24 hours of awareness of the event to meet regulatory and patient safety obligations. For additional details on reporting of safety reports please refer to the Investigator Study Manual.

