7.1 Primary Endpoint

1. *Type, frequency, severity, duration, and relationship to ADVM-043 of adverse events (AEs) of interest and serious adverse events (SAEs) related to ADVM-043.*

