7.2 Secondary Endpoints

Not applicable

8 Statistical Methods

All analyses will be done using SAS (version 9.4, [REDACTED]).

Safety endpoints will be analyzed in a descriptive manner. Continuous data will be reported using the following descriptive statistics:

1. Number of observations (n)
2. Mean and Standard deviation (SD)
3. Median
4. Minimum (min) and Maximum (max)

Minimum and maximum values will be reported in the units of collection with 3 decimals being maximum value; the mean will be presented with 1 decimal place more and the standard deviation 2 decimal places more than the units of collection. Categorical data will be presented using frequency (n = number of subjects; m = number of events) and percentage (%).

Listings will be provided for all data recorded in eCRF to study subject profiles. All listings will be sorted by cohort, subject ID, and date (if applicable). Unscheduled visit data will only be listed and not included in summaries.

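### The SAP contradicts itself on whether related SAEs outside the AE-of-interest list are summarised, and its severity summary omits them on any reading

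*Protocol*

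**What the plan says.** **Endpoint.** Protocol 2.2.1 and SAP 7.1 define the primary endpoint as the type, frequency, severity, duration and relationship of "adverse events (AEs) of interest and serious adverse events (SAEs) related to ADVM-043".

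**Collection in the protocol.** For non-serious events, protocol 6.2 says "Only AEs of interest should be collected and reported", and gives four items: new malignancy, neurologic disorder, rheumatologic or other autoimmune disorder, and unexpected hospitalization. For serious events, 6.3 says "Only SAEs related to ADVM-043 should be collected and reported". Section 5.2 applies the same limit at each assessment ("Review SAEs related to ADVM-043 including type, frequency, severity"), as does 6.8 ("The Investigator must report a related SAE to the Sponsor within 24 hours of awareness of the event"). Section 6.5, however, says of the causality assessment that "it is not a factor in determining what is or is not reported".

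**Scope in the SAP.** Four places include related SAEs: the section 5 schedule, the opening sentence of 11.7, row 5 of the overall table in 11.7.1.1, and one of the tables in 11.7.1.2. Two sentences do not. Section 10.6 restricts what is collected and reported to AEs of interest, and the last sentence of 11.7 restricts what is summarised in the same way. The most-intense-severity flag in 10.6 and the Grade 1-5 table in 11.7.1.3 are also written for AEs of interest only. Section 8 of the SAP promises that "Listings will be provided for all data recorded in eCRF".

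**Deaths.** Protocol 4.3 names Death among four withdrawal circumstances and says "the reason(s) for withdrawal are to be recorded on the CRF". SAP 11.1 lists eight reasons for not completing, and Death is not one of them.

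**The concern.** This is a descriptive safety study, so its result is the set of AE tables. If a programmer follows the two restrictive sentences, part of the primary endpoint (related SAEs outside the list) leaves the summaries. If the programmer follows the table labels, most of it stays. The SAP does not say which prevails. The severity gap does not depend on that choice, because no sentence or label brings such an event into the severity flag or the graded table.

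The lesser risk is misreading. The rows for serious and fatal events in 11.7.1.1 carry no qualifier, so a zero in the fatal row could be taken to mean that nobody died.

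**Working it through.** No arithmetic beyond counting applies. SAP 4.2 gives no sample size and the documents give no event rates. The check traces one kind of event through the planned outputs.

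**Step 1: which event is affected.** It must meet a seriousness criterion in protocol 6.3, be judged related to ADVM-043, and fall outside the four items in 6.2. Unexpected hospitalization is on the list, so many SAEs are collected whatever their cause. What remains is, for example, a related life-threatening or disabling event without an unexpected hospitalization that is not a malignancy, neurologic or autoimmune event.

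**Step 2: where that event is counted.**

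| SAP output | Scope in its label | Counted, by label | Counted, if the last sentence of 11.7 governs |
|---|---|---|---|
| 11.7.1.1 row 1 | AEs of interest | no | no |
| 11.7.1.1 row 2 | related AEs | yes | no |
| 11.7.1.1 row 3 | grade 3 or higher | if graded so | no |
| 11.7.1.1 row 4 | serious | yes | no |
| 11.7.1.1 row 5 | related serious | yes | no |
| 11.7.1.1 row 6 | fatal | if fatal | no |
| 11.7.1.2, first table | AEs of interest | no | no |
| 11.7.1.2, second | related AEs of interest | no | no |
| 11.7.1.2, third | serious AEs of interest | no | no |
| 11.7.1.2, fourth | related serious AEs | yes | no |
| 11.7.1.3 | AEs of interest by Grade 1-5 | no | no |

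- Summaries by system organ class and preferred term: 4 + 1 = 5. Worded for AEs of interest: 3 + 1 = 4. The event enters 5 - 4 = 1 of 5 by label, and 0 of 5 under the restrictive sentence.
- Overall table, by label: rows 2, 4 and 5 always, so 3 of 6. A fatal event (Grade 5) adds rows 3 and 6, so at most 5 of 6. Under the restrictive sentence: 0 of 6.
- Grade 1-5 table: 0 of 1 on both readings.

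**Step 3: whether the data survive.** Protocol 6.8 puts related SAEs on the CRF, and SAP section 8 lists all eCRF data. The loss is from summaries only.

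**Step 4: deaths.** Of the four circumstances in protocol 4.3, three have a counterpart in SAP 11.1 (lost to follow-up, withdrawal of consent, sponsor termination), so 4 - 3 = 1 is missing. Consider one on-study death judged unrelated and outside the 6.2 list. It has no AE record, so it adds 0 to the fatal row and 0 to the listing of deaths due to AEs. It adds 1 to disposition, under Other or Adverse event.

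**Step 5: protocol 6.5 against 6.3, 6.8 and 5.2.** Section 6.5 speaks of an AE without limiting itself to events already in scope, and every SAE is an AE. Under 6.3, the causality judgement alone decides whether an SAE outside the list is collected. Read as written, the two conflict. Read as applying only to events already in scope, 6.5 is harmless, but it does not say so.

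**The case against.** The strongest defence is that the SAP plainly intends to analyse related SAEs. Section 11.7 opens by naming them and adds that all safety data will be listed and summarised. Row 5 of 11.7.1.1 is a count of them, 11.7.1.2 tabulates them, and the schedule records them at every timepoint. The sentence in 10.6 closely follows protocol 6.2, which leaves SAEs to 6.3. All of this stands. A reader who sees only the two restrictive sentences might infer that the SAP drops related SAEs from its analysis. The planned tables do not support that. The fault is a contradiction, and it needs resolving because nothing ranks the sentences against the labels. By label, row 3 even carries some severity information. What the defence does not reach is the severity flag and the graded table.

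On deaths, the SAP 11.1 list includes Other, disposition is listed by subject, and protocol 6.10 asks for an autopsy after any on-study death. So a death is not lost, and the missing reason is a minor mismatch. The serious and fatal rows nowhere claim to count all SAEs or all deaths, so a footnote is enough.

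On 6.5, the related-only rule is otherwise applied consistently and matches the endpoint. Protocol 10.0 mentions SAE reports without that limit but defers to the specifics of the protocol, which leads back to 6.8. A reader might infer that 6.5 obliges the sponsor to collect every SAE. The documents do not support that, because unrelated SAEs outside the list are not in the endpoint and would not change its counts.

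**Conclusion.** The point holds as an internal inconsistency on the primary endpoint and should be fixed. Two SAP sentences exclude related SAEs outside the list, while the endpoint and several planned outputs include them. Depending on which text is followed, such an event enters 1 or 0 of 5 summaries by system organ class and preferred term. On either reading it is absent from the severity flag and the Grade 1-5 table, although severity of related SAEs is part of the endpoint.

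The practical size cannot be computed and may be zero, since the list already captures unexpected hospitalization and no data are lost. The conclusion rests on the text of the two documents. The CRF and study manual were not available and could settle how a death is recorded.

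The missing Death reason and the protocol 6.5 conflict are real but secondary.

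**What to change.** 1. In SAP 10.6 and the last sentence of 11.7, state the scope as AEs of interest together with SAEs related to ADVM-043.
2. Extend the 10.6 severity flag and the 11.7.1.3 table to that scope.
3. Footnote rows 4 and 6 of 11.7.1.1 as counts within the collected scope, not of all SAEs or all deaths.
4. Add Death to the reasons in SAP 11.1, to match protocol 4.3.
5. Reconcile protocol 6.5 with 6.3, 6.8 and 5.2, for example by a sentence limiting 6.5 to events within the collection scope.

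Collecting all SAEs with relatedness as an attribute, or reporting all on-study deaths with date and cause, is open to the sponsor but is not a required correction.

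The cost is low: scope wording, labels, one disposition reason and one clarifying protocol sentence, with no new visits or procedures. The optional routes would add a few forms, and a death date and cause field if the CRF lacks one.
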